1. OBJECTIVES

- 1.1 To determine the maximum tolerated dose of methoxyamine given in conjunction with temozolomide in patients with and without CNS disease.
- 1.2 To determine the dose limiting toxicities of the combination of methoxyamine and temozolomide in patients with and without CNS disease.
- 1.3 To determine the pharmacokinetics of these two agents when given alone or in combination, as well as the pharmacokinetic profile of methoxyamine after a single one-hour IV administration.
- 1.4 To determine relative DNA damage, as single or double strand breaks by comet assay in blood mononuclear cells which will serve as a surrogate for tumor response to the drug combination.

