7. CORRELATIVE/SPECIAL STUDIES

This protocol will utilize the Translational Research Core (TRC) of the Case Comprehensive Cancer Center for the collection, processing, storage, and distribution of patient samples before and after therapy.

**Translational Research Core
ATTN [name]
University Hospitals of Cleveland
[name]
[name]
[name]
[contact]
[contact]
[name]
E-mail: [contact]**

The TRC will schedule patient sample collection in direct communication with the clinical trials research nurse. For UH patients a representative from the TRC will be present during patient sampling, wherein every sample will be given a patient identifier, and collected in the appropriate tubes or vials.

1. Pharmacokinetic studies

PK blood sampling schedule for Temozolomide (TMZ) and Methoxyamine (MX) during cycle 1 are shown in the table that follows. Depending upon the PK data from initial patients, the timing of blood draws for correlative studies may be revised for future patients. PK data during and following single one-hour MX infusion may be obtained in all subsequent cycles (cycles 2 and beyond) as necessary.

Preclinical data have not provided any evidence of significant drug interactions between TMZ and MX. However, this needs to be confirmed. TMZ is not stable in plasma, so plasma sample isolation must be carried out without delay. Plasma from one tube of whole blood will be used for both TMZ and MX determinations.

Collection Instructions for MX and TMX determinations:

1. Draw 5 ml of blood into a lithium heparinized, chilled syringe.
2. Immerse the tube in an icewater bath for 2 min.
3. Centrifuge at 1500 x g and 4 deg. C. for 5 min.
4. Transfer 1.0 ml of plasma into each of two Nunc brand cryostorage tubes.
5. To one tube, to be used for TMZ determination, add 0.1 ml of cold 1 M HCl.
6. Cap, mix, label, and store frozen at -60°C.

a) Methoxyamine determination

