12. STATISTICAL CONSIDERATIONS

For cohort A, a maximum of 36 patients can theoretically participate on this study, based on 6 dose levels with a maximum of 6 patients at each dose level. However, given the fact that a 10-fold increase in MX is being tested in 6 consecutive dose escalation levels it is highly unlikely that the maximum number of patients will need to be enrolled at each level.

For cohort B, a maximum of 42 patients can theoretically participate on this study, based on 7 dose levels with a maximum of 6 patients at each dose level. However, given the fact that a 1.5-fold increase in TMZ and a 10-fold increase in MX is being tested in 7 dose escalation levels it is highly unlikely that the maximum number of patients will need to be enrolled at each level.

The following table gives the probabilities of escalating under given true but unknown underlying rates of DLT:

True Underlying DLT Rate	0.1	0.2	0.3	0.4	0.5
Escalate to next full dose	0.91	0.71	0.49	0.32	0.17
Do not escalate; prior dose level is MTD	0.09	0.29	0.51	0.68	0.83

Thus, if the true underlying rate of DLT is 20%, there will be a 71% chance of escalating to next full dose and a 29% chance that the lower dose will be chosen as the MTD.

The baseline levels (at 0h) of AP sites and DNA strand breaks will be compared to the levels at various time points (i.e. 2h, 4h and 122h) after treatment by paired T-test or Wilcoxon rank sum test. The predictive value of PK parameters (e.g. AUC, C_{max}), levels of AP sites and levels of DNA strand breaks on clinical response and grade 3/4 toxicity will be examined by logistic regression after adjusting the dose level; their predictive value on time to event outcomes, such as disease progression free survival, will be tested using (extended) Cox model after controlling other factors including dose level.

REFERENCES

1. L Liu, P Taverna, CM Whitacre, S Chatterjee, and SL Gerson. Pharmacologic disruption of base excision repair sensitizes mismatch repair-deficient and -proficient colon cancer cells to methylating agents. *Clin Cancer Res* 5:2908-2917, 1999.
2. L Liu, Y Nakatsuru, and SL Gerson. Base excision repair as a therapeutic target in colon cancer. *Clin Cancer Res* 8:2985-2991, 2002.
3. L Liu, JR Donze, and SL Gerson. Methoxyamine enhances antitumor efficacy of BCNU in colon tumor xenografts. *Proc Amer Assoc Cancer Res* 43:794 (#3938), 2002.

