APPENDIX B

Submitted Abstract:

Unexpected prolonged half life of the base-excision repair inhibitor Methoxyamine (MX) given with Temozolomide (TMZ) in the first in human phase 1 clinical trial

Author Block: *[name], [name], [name], [name].* Ireland Cancer Ctr., Cleveland, OH, Ireland Cancer Center, Cleveland, OH

Abstract:

Background: MX is the first base excision repair (BER) inhibitor evaluated in humans. MX blocks the BER pathway by covalently binding to apurinic/pymidinic (AP) sites in DNA. In several preclinical studies, improved therapeutic efficacy has been demonstrated with various chemotherapeutic agents including alkylating agents, such as TMZ. Initial results and correlative studies of the first in humans administration of MX are presented.

Methods: This ongoing phase I dose-escalation trial investigates the safety, pharmacokinetic (PK) and pharmacodynamic (PD) profile of MX given as an intravenous continuous infusion (CI) for 5 days in combination with TMZ given orally for 5 days on a 28-day cycle. PD markers, including analysis of AP sites measured on DNA extracted from patients' mononuclear cells (PBMCs) as well as DNA strand break determined by comet assay at multiple time points during the 5-day treatment with MX and TMZ, are included.

Results: 5 patients with metastatic solid tumors have enrolled, 4 at dose-level (DL) 1 (TMZ 100 mg/m²/day, x5days and MX 15 mg/m²/day, x5days CI) and 1 at DL 2 (TMZ 150 mg/m²/day, x5days, MX at same dose as in DL 1). Primary tumors include colon cancer (n=2), head and neck cancer (n=1), radiation-associated sarcoma (n=1), thymic carcinoma (n=1). Treatment has been well tolerated. No treatment-related AEs leading to dose reduction, interruption or discontinuation were reported. No grade 3 or higher treatment related toxicities or AEs have occurred. Grades 1-2 toxicities observed include: nausea, vomiting, fatigue, fever, dyspnea on exertion, anemia, leukopenia, lymphopenia, hypophosphatemia, dyspnea on exertion, nystagmus.

PK analyses on samples from the 5 patients included in the study revealed a distinct PK profile different from the one observed in rats and dogs, where half-life of MX was estimated to be 19 minutes and 4.5 hours respectively. In humans, MX half life is estimated to be 45.3 hours (range: 32 - 68.8 hours).

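### Section 12 names an unpaired rank test for paired 0h versus post-dose samples, and its 122h time point and AP-site levels have no sampling plan in Section 7

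*Combined protocol and SAP*

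**What the plan says.** Section 12 (Statistical Considerations) sets the comparison as follows: "The baseline levels (at 0h) of AP sites and DNA strand breaks will be compared to the levels at various time points". It then lists the times and tests: "at various time points (i.e. 2h, 4h and 122h) after treatment by paired T-test or Wilcoxon rank sum test". It goes on to use the same markers as predictors: "levels of AP sites and levels of DNA strand breaks on clinical response and grade 3/4 toxicity will be examined by logistic regression". The same sentence carries them into a Cox model for time-to-event outcomes.

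Objective 1.4 is narrower: "To determine relative DNA damage, as single or double strand breaks by comet assay in blood mononuclear cells". It does not name AP sites.

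Section 7 (Correlative/Special Studies) sets out two studies, pharmacokinetics and the comet assay. Its table draws comet samples at 0, 2h, 4h and 24h, and PK samples at 0, 30 min, 1h, 2h, 4h, 8h, 24h, 48h, 72h, 96h and 120h. It allows that "the timing of blood draws for correlative studies may be revised for future patients". The study calendar (Section 8) refers back to Section 7 for the correlates and adds no time point.

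Appendix B, an abstract on the earlier 5-day infusion schedule, does report "analysis of AP sites measured on DNA extracted from" patients' mononuclear cells.

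**The concern.** The 0h and post-dose values come from the same patient. Section 12 recognises this by listing a paired t-test, but the nonparametric option beside it assumes two independent samples. No rule says when each test applies, so an analyst following the plan could run the unpaired one.

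The paragraph also does not match the samples. One of its three contrasts has no scheduled draw, one scheduled draw has no contrast, and the AP-site analyses have no stated assay or schedule.

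Objective 1.4 treats the comet result as a surrogate for tumour response. As written, its analysis cannot be carried out in full, and the gaps would have to be filled after data are in hand.

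**Working it through.** The plan gives no sample size, alpha, SD, correlation or effect size for these tests, so there is no stated figure to reproduce. The first two steps compare text with text; the third is an illustration on assumed inputs.

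**1. Times**

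| Time | Comet row (Section 7) | PK row (Section 7) | Contrast with 0h (Section 12) |
|---|---|---|---|
| 2h | yes | yes | yes |
| 4h | yes | yes | yes |
| 24h | yes | yes | no |
| 120h | no | yes (last) | no |
| 122h | no | no | yes |

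Section 12 introduces its list with i.e., so the list defines the contrasts and does not merely give examples.

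**2. AP sites**

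Section 7 mentions AP sites twice: as one source of the breaks the comet assay detects, and in earlier in vitro work where strand breaks correlated with AP-site levels. Neither is a planned measurement. A comet reading cannot stand in for an AP-site level:

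- Section 7 says the assay also picks up other alkali-labile adducts.
- Section 12 lists the two markers separately.
- In Appendix B they moved in opposite directions under the combination: at least 60% fewer detectable AP sites, but 1.5- to 3-fold more strand breaks.

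**3. Size of the test error**

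Take SD σ at each time, within-patient correlation ρ, shift δ and n pairs. The mean difference has variance 2σ²(1−ρ)/n. An unpaired test scales it by 2σ²/n, so under the null its statistic has SD √(1−ρ) instead of 1.

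Hand check by normal approximation, with ρ = 0.5, n = 20, δ = 0.5σ and two-sided 0.05:

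- Unpaired: mean of statistic 0.5 × √(20/2) = 1.58, SD √0.5 = 0.707. Power ≈ P(Z > (1.96 − 1.58)/0.707) = P(Z > 0.54) ≈ 0.30. Type I error ≈ 2 × P(Z > 1.96/0.707) = 2 × P(Z > 2.77) ≈ 0.006.
- Paired: mean of statistic 0.5 × √20/√(2 × 0.5) = 2.24. Power ≈ P(Z > 1.96 − 2.24) = P(Z > −0.28) ≈ 0.61.

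Simulation (10,000 data sets per setting, two-sided 0.05; lognormal rows assume a log-SD of 0.8, with the shift on the log scale):

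| Data | n | ρ | Shift (SD) | Rank sum | Signed-rank | Paired t |
|---|---|---|---|---|---|---|
| Normal | 20 | 0 | 0.5 | 0.328 | 0.311 | 0.327 |
| Normal | 20 | 0.3 | 0.5 | 0.291 | 0.418 | 0.435 |
| Normal | 20 | 0.5 | 0.5 | 0.276 | 0.542 | 0.566 |
| Normal | 20 | 0.7 | 0.5 | 0.240 | 0.763 | 0.785 |
| Normal | 20 | 0.5 | 1.0 | 0.915 | 0.985 | 0.989 |
| Normal | 10 | 0.5 | 1.0 | 0.529 | 0.786 | 0.802 |
| Normal | 36 | 0.5 | 0.5 | 0.544 | 0.817 | 0.832 |
| Lognormal | 20 | 0.5 | 0.5 | 0.268 | 0.497 | 0.415 |
| Lognormal | 20 | 0.5 | 1.0 | 0.919 | 0.972 | 0.917 |

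For normal data with n = 20, rank sum type I error at ρ = 0, 0.3, 0.5 and 0.7 is 0.046, 0.022, 0.009 and 0.002. With positive correlation the test is therefore conservative and loses power. The lognormal rows matter most, because skewed data are where a nonparametric test would be chosen.

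**The case against.** The strongest reply is about weight.

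- **Wording slip.** The authors clearly knew the data were paired and put a valid test first, so rank sum may be a slip for signed-rank. That is plausible, and the power loss arises only if the nonparametric route is taken and the named test is run. The text as it stands still permits that.
- **One misprint.** If 122h is a misprint for 24h, both time-point problems vanish with one correction. It could equally be left over from the 5-day schedule; the documents do not say. The permission to revise draw times does not create a 122h sample.
- **Effect size.** A 0.5 SD shift sits at the low end of the nearest evidence. At the assumed log-SD of 0.8, the 1.5- to 3-fold range in Appendix B corresponds to ln(1.5)/0.8 = 0.51 SD up to ln(3)/0.8 = 1.37 SD, with 2-fold at ln(2)/0.8 = 0.87 SD. These fold changes are against a single TMZ dose, not 0h, so they are a rough guide only. For lognormal data with correlation 0.5 (4,000 data sets per setting), a 2-fold change gives rank sum 0.81 versus signed-rank 0.91 at n = 20, and 0.98 versus 0.995 at n = 36; a 3-fold change at n = 20 gives about 1.00 for both. At n = 10 a 2-fold change still gives 0.38 versus 0.60. So the loss is material for few patients or small changes and modest otherwise.

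These points limit the importance of the test name. They do not answer the AP-site gap.

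**Conclusion.** The point holds in all three parts. The nonparametric test named is the wrong one for paired data, the 122h contrast has no sample while the 24h sample has no contrast, and the AP-site analyses have no assay or schedule in Section 7. Which section is in error cannot be settled from the documents.

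The text mismatches rest on no assumption. The power figures do: n, correlation, SD and shift are all assumed, and they show direction and rough size only. Under positive correlation the risk is a missed pharmacodynamic signal, not a false one.

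The paragraph should be corrected before the correlative analysis, both so that the right test is run and so that the listed contrasts and the AP-site terms in the logistic and Cox models correspond to data that will exist.

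**What to change.** Reword the comparison in Section 12 as within-patient change from 0h at 2h, 4h and 24h, tested by paired t-test or Wilcoxon signed-rank test, and say when each is used.

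Delete 122h or, if a late comet sample is intended, add it to the Section 7 table.

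Reconcile the two sections on AP sites. If they are not measured, remove them from the baseline comparison and from the logistic and Cox models. If they are measured, add the assay and its sampling times to Section 7.

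State also which patients are pooled for the test. The smallest two-sided exact signed-rank p-value is 2/2ⁿ: 0.25 for 3 pairs, 0.0625 for 5 and 0.031 for 6. A dose level with fewer than 6 pairs therefore cannot reach 0.05 on its own.

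The cost is one paragraph and no new samples if 122h and AP sites are removed. If either is kept, Section 7 needs additions, and the documents do not show whether the blood already scheduled would suffice.

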3.1 Eligibility Criteria

- 3.1.1 Patients must have a histologically confirmed solid tumor that is considered incurable and is not amenable to conventional surgical, radiation therapy or chemotherapy treatment programs.
- 3.1.2 Prior chemotherapy and/or radiation are allowed. At least 3 weeks must have elapsed since prior large-field radiation therapy; patients must have been off previous anti-cancer therapy for at least 3 weeks (6 weeks for mitomycin-C and nitrosoureas); and recovered from all treatment related toxicity to \leq grade 1 according to NCI CTCAE version 3.0 (with the exception of alopecia and radiation-induced taste changes). Prior temozolomide treatment is not restricted.
- 3.1.3 Age \geq 18 years.
- 3.1.4 ECOG performance status \leq 2 (Karnofsky \geq 50%, see Appendix A).
- 3.1.5 Life expectancy \geq 12 weeks.

3.1.6 Patients must have normal organ and marrow function as defined below:

- absolute neutrophil count	$\geq 1,500/\mu\text{l}$
- platelets	$\geq 100,000/\mu\text{l}$
- hemoglobin	$\geq 10.0 \text{ g/dl}$
- total bilirubin	$\leq 1.5 \text{ mg/dl}$
- AST(SGOT) normal	$\leq 2.5 \times \text{institutional upper limit of}$
- creatinine	$\leq 1.5 \text{ mg/dl}$
	and/or
- creatinine clearance	$\geq 60 \text{ mL/min}/1.73 \text{ m}^2$

3.1.7 Patients with known primary or metastatic CNS disease, are eligible for participation in cohort B, but not in cohort A.

3.1.8 Women of child-bearing potential and men must agree to use adequate contraception (hormonal or barrier method of birth control; abstinence) prior to study entry and for the duration of study participation. Should a woman become pregnant or suspect she is pregnant while participating in this study, she should inform her treating physician immediately.

3.1.9 Ability to understand and the willingness to sign a written informed consent document.

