An increase in formation of AP sites over time in cells was detected after patients received a single dose of TMZ (100 mg/m²), reaching the highest levels 2 or 4 h after TMZ in different patients.

Administration of the combination of TMZ and MX resulted in at least 60% reduction in detectable AP sites, due to the binding of MX to AP sites to form MX-bound AP sites.

Comet assay in PBMCs following treatment with the combination of MX and TMZ detected a 1.5 to 3-fold increase of DNA strand breaks compared to single dose of TMZ.

Conclusions: Initial data from the first in humans MX phase I clinical trial demonstrate that MX in combination with TMZ is well tolerated. MX has a distinct PK profile in humans, corresponding to a 10-fold increase in estimated half-life when compared to the half-life observed in dogs. PD demonstration of MX's biologic activity on patients' mononuclear cells has been demonstrated even at the first dose level.

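### Section 12 does not tie the DNA-damage predictors in its outcome models to each patient's own 0 h value

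*Combined protocol and SAP*

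**What the plan says.** Section 12 has two biomarker sentences. The first is a before/after test: "The baseline levels (at 0h) of AP sites and DNA strand breaks will be compared to the levels at various time points" following treatment. The second turns to outcomes. There the markers appear simply as levels: the predictive value of PK parameters and "levels of AP sites and levels of DNA strand breaks on clinical response and grade 3/4 toxicity will be examined by logistic regression". The only adjuster named is dose level: the predictive value "will be examined by logistic regression after adjusting the dose level". For progression-free survival and similar endpoints, the predictive value "will be tested using (extended) Cox model after controlling other factors including dose level". Neither model sentence gives a time point, a change score, a ratio or a 0 h covariate, and no other section supplies one.

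Three other places bear on this:

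- Objective 1.4 is "To determine relative DNA damage, as single or double strand breaks by comet assay in blood mononuclear cells", intended as a surrogate for tumor response to the combination.
- The sampling table in Section 7 schedules comet samples at 0, 2, 4 and 24 h in cycle 1. It lists no AP-site samples.
- Section 3.1.2 allows earlier chemotherapy and radiation, with a washout of 3 weeks for most therapy, and adds: "Prior temozolomide treatment is not restricted". Section 2 expects many patients with brain disease to have had temozolomide already.

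**The concern.** On the log scale, a post-dose strand-break level is the sum of what the patient brought to the study and what the drugs added. The second part is the one of interest. Entry criteria that admit varied prior DNA-damaging treatment make it likely that the first part differs between patients. Adjusting for assigned dose level cannot remove a difference that exists before dosing.

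Two things could go wrong. If induced damage drives toxicity or response, spread in the 0 h values dilutes the predictor and hides the association. If instead the 0 h damage is what relates to outcome, for example as a marker of heavy pretreatment, the model could credit the drug combination with predictive value that it does not have.

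**Working it through.** **Plan's own figures.** Section 12 gives no power, alpha or effect size for these models, so there is nothing to reproduce on this point. Its only operating characteristics are the escalation probabilities. The formula (1−p)³ + 3p(1−p)²(1−p)³ gives 0.906, 0.709, 0.494, 0.309 and 0.172, against the stated 0.91, 0.71, 0.49, 0.32 and 0.17. They have no bearing on the biomarker models.

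**Inputs from the documents.** Section 12 gives maximum enrolment of 36 (cohort A) and 42 (cohort B); 36 + 42 = 78. The logistic adjuster is dose level.

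**Assumed, because the documents are silent.** Two-sided 5% test; 25% event rate; odds ratio 2.5 per SD of the component that drives outcome; six equal dose groups; 0 h level B and induced change D independent; variance ratio r = var(B)/var(D) from 0.25 to 3.

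**Model.** Post-dose log level L = B + D. If D drives outcome, the correlation of L with D is 1/√(1+r): 0.89 at r = 0.25, 0.71 at r = 1 and 0.50 at r = 3.

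**Power when induced damage drives outcome** (logistic model with dose level, likelihood-ratio test, 2,000 simulated trials per cell, Monte Carlo error about 1 point):

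| N | r | Level, no 0 h term | Change from 0 h | Level + 0 h covariate |
|---|---|---|---|---|
| 36 | 0.25 | 52% | 62% | 62% |
| 36 | 1 | 33% | 60% | 62% |
| 36 | 3 | 19% | 60% | 62% |
| 78 | 0.25 | 82% | 91% | 91% |
| 78 | 1 | 62% | 91% | 92% |
| 78 | 3 | 37% | 91% | 91% |

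**Hand check at N = 78.** Power of 91% corresponds to a mean z of about 1.96 + 1.34 = 3.30. Multiplying by the correlation:

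- r = 0.25: 3.30 × 0.89 = 2.94, and Φ(2.94 − 1.96) = Φ(0.98) = 84%
- r = 1: 3.30 × 0.707 = 2.33, and Φ(0.37) = 64%
- r = 3: 3.30 × 0.50 = 1.65, and Φ(−0.31) = 38%

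These agree with the simulated 82%, 62% and 37% to within about 2 points.

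**Low end of baseline spread.** A separate simulation used log-scale SDs of 0.10 (baseline), 0.30 (induced) and 0.10 (assay), so r = 0.10²/0.30² = 0.11, with odds ratio 2 and 25% events. Power for unreferenced level, 0 h covariate and log ratio was 54%, 56% and 53% at N = 60, and 63%, 65% and 62% at N = 78: essentially no loss. With baseline SD 0.15 the loss was about 4 to 7 points. With baseline SD 0.30 (r = 1) and N = 60 it was 33% against 52%, or 19 points.

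**False positives when D has no effect but B is prognostic** (odds ratio 2.5 per SD of B):

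| N | r | Level, no 0 h term | Change or 0 h-adjusted |
|---|---|---|---|
| 36 | 1 | 37% | 7–8% |
| 36 | 3 | 50% | 7% |
| 78 | 1 | 63% | 5–6% |
| 78 | 3 | 80% | 6% |

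At the smaller spreads (baseline SD 0.10 to 0.15, odds ratio 2) the unreferenced level gave 11 to 20%. If neither B nor D relates to outcome, all three models stay at 5 to 8%.

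**When the ratio costs something.** With assay SD s, the log ratio has variance var(D) + 2s², and the single level has var(D) + var(B) + s². The ratio is the cleaner measure of D whenever the SD of B exceeds s, and slightly noisier below that.

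**The case against.** A reader might infer that Section 12 prescribes raw post-dose levels. It does not: neither word appears in the model sentence, the preceding sentence is a within-patient comparison with 0 h, Objective 1.4 speaks of relative damage, and the Cox model's other factors could include the 0 h value. That stands. The fair charge is that the predictor is left undefined and its plain reading is unreferenced. It is still more than a missing definition, because the logistic model names one adjuster and a better method is available from a sample already scheduled.

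A reader might also size the effect from Appendix B, where the comet assay "detected a 1.5 to 3-fold increase of DNA strand breaks compared to single dose of TMZ", and take that range as the between-patient spread of induced change. The documents do not support this. The comparison is with temozolomide alone, not with 0 h. It comes from a 5-day continuous methoxyamine infusion, and nothing says that the range is one value per patient. The 0.30 in the low-end check is therefore only illustrative.

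Two further inferences go too far. Low power cannot be put down to this omission alone: at N = 36 even the referenced models reach only 60 to 62% under the assumptions used, Section 12 thinks full enrolment highly unlikely, and response is assessed only in patients with measurable disease. And false predictive claims are not shown to be likely: they need prognostic 0 h damage, which is plausible given the entry criteria but not documented.

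Finally, these are correlative analyses that drive no dose decision. That limits the priority but does not remove the point.

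**Conclusion.** The point holds in a conditional form. As written, the outcome models do not separate damage present at 0 h from damage induced by the drugs, although the objective concerns relative damage and the 0 h comet sample is scheduled. How much this costs turns on the ratio of baseline to induced variance, which the documents do not give. The loss is negligible at r near 0.1, about 9 points at r = 0.25, roughly 20 to 30 points at r = 1, and up to about 54 points at r = 3 with N = 78. These figures assume odds ratios of 2 to 2.5 per SD, 25% events and independence of baseline and induced change. Inflation of false predictive findings is a separate condition: it arises only if 0 h damage is itself related to outcome. The analyses affected are secondary; the MTD and DLT objectives are untouched.

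**What to change.** In Section 12, define the strand-break predictor in both the logistic and the Cox models as the log change from the patient's own 0 h value, or enter the post-dose log level with the log 0 h value as a covariate. Name one time point or one summary in advance, chosen from the 2, 4 and 24 h comet samples in Section 7, and give the reason. Averaging 2 h and 4 h because Appendix B describes AP sites "reaching the highest levels 2 or 4 h after TMZ in different patients" is not a sufficient reason: that peak follows temozolomide alone, concerns a different marker, and would leave the 24 h sample unused. If induced change may depend on the 0 h level, the covariate form is preferable because it holds that level fixed.

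Apply the same rule to AP sites only if 0 h and post-dose AP-site samples are actually collected; Section 7 schedules none.

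The cost is a one-sentence amendment, with no new samples for strand breaks. Statistically it is at most one extra covariate per model (none with the log ratio), and slightly more assay noise in the ratio if baseline variation is very small.
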